8.1 Adverse Events (AEs)

Definition: any unfavorable medical occurrence in a human subject who receives ¹⁸F-FNP-PET/CT and / or estradiol as part of the estradiol challenge for research purposes only, including any abnormal sign, symptom, or disease. The event does not necessarily have to be causally related to injection of ¹⁸F-FNP or PET/CT imaging to qualify as an adverse event, just temporally related.

Grading: The descriptions and grading scales found in the revised NCI Common Terminology Criteria for Adverse Events (CTCAE) version 4.0 will be utilized for all toxicity reporting. A copy of the CTCAE version 4.0 can be downloaded from the CTEP website.

Attribution (relatedness), Expectedness, and Seriousness: the definitions for the terms listed that should be used are those provided by the Department of Health and Human Services' Office for Human Research Protections (OHRP). A copy of this guidance can be found on OHRP's website: (<http://www.hhs.gov/ohrp/policy/AdvEvtGuid.htm>).

8.2 Unanticipated Problems

Definition:

- Unexpected (in terms of nature, severity, or frequency) given (a) the research procedures that are described in the protocol-related documents, such as the IRB-approved research protocol and informed consent document; and (b) the characteristics of the subject population being studied;
- Related or possibly related to participation in the research (in this guidance document, possibly related means there is a reasonable possibility that the incident, experience, or outcome may have been caused by the procedures involved in the research); and
- Suggests that the research places subjects or others at a greater risk of harm (including physical, psychological, economic, or social harm) than was previously known or recognized.

8.3 Noncompliance

Definition: failure to follow any applicable regulation or institutional policies that govern human subjects research or failure to follow the determinations of the IRB. Noncompliance may occur due to lack of knowledge or due to deliberate choice to ignore regulations, institutional policies, or determinations of the IRB.

8.4 Serious Noncompliance

Definition: noncompliance that materially increases risks that result in substantial harm to subjects or others, or that materially compromises the rights or welfare of participants.

8.5 Protocol Exceptions

Definition: A planned deviation from the approved protocol that are *under the research team's control*.

Exceptions apply only to a single participant or a singular situation. Research imaging protocols which involve the injection of radioactive tracers can produce unique situations not common to standard treatment protocols. In the event a situation occurs which requires deviation from this protocol- for example less than expected tracer production, problems with the scanner, patient unable to tolerate the imaging protocol as described,- the principal investigator will have final authority over whether or not a study is completed. Any protocol deviations will be documented on the PET imaging data form. Deviations such as less than expected tracer production can be accounted for during data analysis and will not necessarily result in cancellation of the scan

Except as described above, pre-approval of protocol exceptions must be obtained prior to the event.

8.6 Reporting to the Human Research Protection Office (HRPO) and the Quality Assurance and Safety Monitoring Committee (QASMC) at Washington University

The PI is required to promptly notify the IRB of the following events:

- Any unanticipated problems involving risks to participants or others which occur at WU, any BJH or SLCH institution, or that impacts participants or the conduct of the study.
- Noncompliance with federal regulations or the requirements or determinations of the IRB.
- Receipt of new information that may impact the willingness of participants to participate or continue participation in the research study.

These events must be reported to the IRB within 10 working days of the occurrence of the event or notification to the PI of the event. The death of a research participant that qualifies as a reportable event should be reported within 1 working day of the occurrence of the event or notification to the PI of the event.

8.7 Timeframe for Reporting Required Events

Deaths	
Any reportable death while on study or within 30 days of study	Immediately, within 24 hours, to PI and the IRB
Any reportable death while off study	Immediately, within 24 hours, to PI and the IRB
Adverse Events/Unanticipated Problems	
Any reportable adverse events as described in Sections 8.1 and 8.2 (other than death)	Immediately, within 24 hours to PI and within 10 working days to the IRB
All adverse events regardless of grade and attribution should be submitted cumulatively	Include in DSM report
Noncompliance and Serious Noncompliance	
All noncompliance and serious noncompliance as described in Sections 8.3 and 8.4	Immediately, within 24 hours, to PI and within 10 working days to the IRB

9.0 DATA AND SAFETY MONITORING PLAN

In compliance with the Washington University Institutional Data and Safety Monitoring Plan, the Principal Investigator will provide a Data and Safety Monitoring (DSM) report to the Washington University Quality Assurance and Safety Monitoring Committee (QASMC) semi-annually beginning six months after accrual has opened (if at least five patients have been enrolled) or one year after accrual has opened (if fewer than five patients have been enrolled at the six-month mark).

The Principal Investigator will review all patient data at least every six months, and provide a semi-annual report to the QASMC. This report will include:

- HRPO protocol number, protocol title, Principal Investigator name, data coordinator name, regulatory coordinator name, and statistician
- Date of initial HRPO approval, date of most recent consent HRPO approval/revision, date of HRPO expiration, date of most recent QA audit, study status, and phase of study
- History of study including summary of substantive amendments; summary of accrual suspensions including start/stop dates and reason; and summary of protocol exceptions, error, or breach of confidentiality including start/stop dates and reason
- Study-wide target accrual and study-wide actual accrual
- Protocol activation date
- Average rate of accrual observed in year 1, year 2, and subsequent years
- Expected accrual end date and
- Objectives of protocol with supporting data and list the number of participants who have met each objective
- Measures of efficacy
- Early stopping rules with supporting data and list the number of participants who have met the early stopping rules

- Summary of toxicities
- Abstract submissions/publications
- Summary of any recent literature that may affect the safety or ethics of the study

The study principal investigator and Research Patient Coordinator will monitor for serious toxicities on an ongoing basis. Once the principal investigator or Research Patient Coordinator becomes aware of an adverse event, the AE will be reported to the HRPO and QASMC according to institutional guidelines.

10.0 STATISTICAL CONSIDERATIONS

10.1 Study Objectives and Endpoints

The primary endpoints of the study are the change in ^{18}F -FFNP uptake following one-day of estradiol measured as the SUV, T/M and tumor-to-normal tissue ratio (T/N), and the response to ET among cancer patients (responders vs. non-responders). The secondary endpoint of the study is the immunohistochemical (IHC) determination of PgR status (PgR+ vs. PgR-) in ER+ breast carcinoma.

Study Design: This is a pilot study aiming to evaluate if response to ET of breast cancer can be predicated by the changes in tumor uptake of ^{18}F -FFNP after a one-day estradiol challenge test. The sampling method is non-random. The change of ^{18}F -FFNP uptake after estradiol will be correlated with responsiveness to ET. Additionally, an optimal threshold of the change in ^{18}F -FFNP uptake will be developed to differentiate therapy responding and non-responding patients. Also, the change in ^{18}F -FFNP uptake after estradiol challenge will be compared with the IHC determination of PgR status with respect to the prediction of ET responsiveness.

Accrual: The rate of accrual for the study is expected to be about 1 - 2 patients per month. It is expected that the accrual period of the study will be completed in 30 months with total 50 patients enrolled.

Power Analysis: It is estimated that the response rate to ET in the recruited patients will range from 20-50%. Using a 2-sided independent t-test with 80% power at a 0.05 significance level, a sample of 10 responders vs. 40 non-responders (i.e., 20% response rate) will allow us to detect a minimum of 101% SD between-group difference, where SD represents a pooled standard deviation of the ^{18}F -FFNP uptake changes among both therapy responding and non-responding patients; and a sample of 25 responders vs. 25 non-responders (i.e., 50% response rate) will allow us to detect a minimum of 80.9% SD between-group difference.

Data Analysis: Demographic and clinical characteristics of all the enrolled patients will be summarized using descriptive statistics. The changes in ^{18}F -FFNP uptake after estradiol challenge will be compared between responders and non-responders via

Wilcoxon rank sum test. A receiver operating characteristic (ROC) curve will be plotted to identify an optimal threshold of ^{18}F -FFNP uptake change to determine a criterion for the future prediction of therapy responsiveness. The positive and negative predictive values (PPV and NPV) will be calculated for response to ET using both the ^{18}F -FFNP uptake-based criterion and IHC determination of PgR receptor status. Multivariate logistic analyses of therapy response will be used to examine prediction power among the changes in ^{18}F -FFNP uptake and PgR receptor status

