We have established the efficacy of this “hormone-challenge test for functional ER” in new mammary cancer models derived from STAT1^{-/-} mice (Fowler A. J Nucl Med. 2012; 53:1119-26). In ovary-intact mice, SSM2 tumors, which are ER⁺ but ET non-responsive, show no decrease in PgR (PgR-A and PgR-B) levels upon antiestrogen with Fulvestrant treatment, whereas SSM3 tumors, which are ER⁺ and ET responsive, show a great reduction in PgR levels. More notably, in the SSM3 ER⁺/ET-responsive tumors, both a large decrease in ¹⁸F-FFNP uptake after Fulvestrant treatment and a large increase in ¹⁸F-FFNP uptake are observed after estradiol. The average tumor-muscle (T/M) ratios increased from 3.6 for the untreated mice to 6.9 in SSM3 mice after 24 hours of estrogen stimulation. Therefore, an up or down change in ¹⁸F-FFNP T/M ratio in mammary tumors accurately predicted sensitivity to estrogen addition or deprivation therapy, respectively, and was able to distinguish between ER⁺/endocrine-responsive and ER⁺/endocrine non-responsive disease.

More recently, Chan et al. (manuscript in preparation) used the same model to follow the decrease in ¹⁸F-FFNP mammary tumor uptake in response to estrogen deprivation therapy by ovariectomy, which reduces tumor PgR levels. Notably, in this study, they compared PET imaging using ¹⁸F-FDG (to measure glucose uptake), ¹⁸F-FES (to measure ER levels), or ¹⁸F-FFNP (to measure PgR levels) to see which probe would best predict response to estrogen deprivation therapy. Uptake in endocrine-sensitive and -resistant mammary tumors (both of which were ER⁺) was measured by PET in mice before ovariectomy, and on days 3 and 4 after this form of estrogen deprivation therapy. Specificity of ¹⁸F-FFNP uptake in ER⁺ mammary tumors was determined by competition assays using unlabeled ligands for PgR and confirmed by IHC. The levels of ¹⁸F-FES and FDG tumor uptake remained unchanged in endocrine-sensitive or resistant tumors after estrogen deprivation therapy compared to those at pre-treatment. By contrast, estrogen deprivation therapy led to a reduction in PgR expression and ¹⁸F-FFNP uptake in endocrine-sensitive tumors, but not in endocrine-resistant tumors, as early as 3 days post-treatment, importantly demonstrating that *PgR-PET provides a more sensitive and robust measure of tumor response than ¹⁸F-FES- or ¹⁸F-FDG-PET.*

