ratio. The SUV is widely used for assessment of regional tracer accumulation in oncological studies, is technically simple to perform, and makes imaging easier for the patient because longer dynamic imaging is not required. SUV is a decay-corrected measurement of activity per volume of tissue (nCi/mL) divided by the average activity per unit mass in the entire body. The absolute change and the percent change in uptake of ^{18}F -FFNP will be assessed semiquantitatively and correlated with the clinical and radiologic results and subsequently with the results of the clinical follow-up evaluation. In patients with multiple lesions, the uptake up to 5 most intense lesions seen on PET images will be determined and the overall average values for all of the known lesions also will be recorded. The changes in SUV and T/N between the baseline and post estradiol challenge FFNP-PET/CT images will be compared in responders and nonresponders. Volumes of interest (VOIs) will be drawn around the entire lesion with the knowledge of the location of the tumor. SUV_{max} will be determined within the VOI. In addition, a similar volume of interest will be drawn in a comparable normal tissue region. The T/N ratio will be calculated by dividing the SUV_{max} of the tumor by the average SUV of normal comparable tissue. The absolute change and the percent change in uptake of ^{18}F -FFNP will be assessed semi-quantitatively and correlated with the clinical and radiologic results and subsequently with the results of the clinical follow-up evaluation. In patients with multiple lesions, the uptake of up to 5 lesions, selected as the most intense lesions seen on PET, will be determined and the overall average values for all of the known lesions also will be recorded. In addition, in patients with multiple lesions, SUV_{max} and T/N ratio will be measured for all known measurable lesions to assess within-patient heterogeneity in ^{18}F -FFNP uptake. Considering the optimum cutoff value for ^{18}F -FFNP uptake that distinguishes responders from nonresponders, lesions will be classified as ^{18}F -FFNP+ for lesions with ^{18}F -FFNP uptake at or greater than the cutoff value and ^{18}F -FFNP- for lesions with ^{18}F -FFNP uptake below the cutoff value. The changes in SUV and T/N after treatment will be compared in responders and nonresponders. The results of the PET studies will not be provided to the patient or the treating oncologist (see above). Clinical follow-up will provide information on tumor response, which will then be correlated with the sequential PET results to determine if these are predictive of ultimate response to estrogen therapy.

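### Section 10.1 lists three FFNP uptake measures as primary together but never names the one variable (metric, scale, lesion summary) that enters the primary test and the ROC cutoff

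*Combined protocol and SAP*

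**What the plan says.** Section 10.1 gives the primary endpoints as the change in FFNP uptake "following one-day of estradiol measured as the SUV, T/M and tumor-to-normal tissue ratio (T/N), and the response to ET among cancer patients". The three uptake measures are not ranked. The power analysis uses one two-sided 0.05 level and 80% power for one unspecified uptake-change variable. The data analysis compares responders with non-responders by a Wilcoxon rank sum test and uses an ROC curve to find an optimal threshold of "uptake change to determine a criterion for the future prediction of therapy responsiveness". Neither step names a metric, and no multiplicity rule appears.

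Section 6.5 describes the measurements:

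- **Metric.** "The changes in SUV and T/N between the baseline and post estradiol challenge FFNP-PET/CT images will be compared in responders and nonresponders". T/N is the SUVmax "of the tumor by the average SUV of normal comparable tissue". T/M is not mentioned. The abbreviation is expanded only in the mouse background of Section 1.3: "The average tumor-muscle (T/M) ratios increased from 3.6 for the untreated mice to 6.9 in SSM3 mice".
- **Scale.** "The absolute change and the percent change in uptake of" FFNP are both to be assessed. Neither is assigned to the responder comparison.
- **Several lesions.** The uptake in "up to 5 most intense lesions seen on PET images will be determined and the overall average values for all of the known lesions" is to be recorded. The text does not say which of these is the patient's value in the test, or which of the two scans determines the most intense lesions.

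The study design paragraph of 10.1 sets the status: "This is a pilot study aiming to evaluate if response to ET of breast cancer can be predicated by the changes in tumor uptake".

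**The concern.** Two analysts could follow this plan faithfully, run different primary tests and publish different cutoffs. One might use percent change in SUVmax over five lesions, the other absolute change in T/N averaged over all known lesions. A listed primary measure, T/M, could not be computed in patients without inventing a rule.

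Two things are at stake. The first is the meaning of the 0.05 level and the 80% power, which fit one test of one variable. The second is the cutoff. It is meant for future prediction, and its PPV and NPV are to be set beside those of PgR by IHC, whose positivity is fixed in advance (Allred score of at least 4, Section 3.1). If the FFNP measure is picked after the data are seen, that comparison tilts towards FFNP.

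**Working it through.** **1. The plan's own figures.** Inputs from 10.1: 10 vs 40 with 1.01 SD, 25 vs 25 with 0.809 SD, two-sided t-test, alpha 0.05. Power is the probability that a noncentral t with 48 degrees of freedom and noncentrality d × √(n1·n2/(n1+n2)) exceeds the critical value.

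- 10 vs 40: 1.01 × √(400/50) = 2.857, power 79.9%.
- 25 vs 25: 0.809 × √(625/50) = 2.860, power 80.0%.

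Both reproduce, for any one metric.

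**2. If any one metric counts as success.** Independent tests give the ceiling: 1 − 0.95² = 9.75% for two and 1 − 0.95³ = 14.3% for three. The measures will be correlated, because SUV and T/N share the tumor SUVmax. The documents give no correlation, so 0.9, 0.7 and 0.5 are assumed. Simulated null false-positive rates use exact Wilcoxon limits (U ≤ 119 for 10/40, U ≤ 211 for 25/25), 100,000 runs and equally correlated normal data:

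| Groups | Metrics | 0.9 | 0.7 | 0.5 |
|---|---|---|---|---|
| 10/40 | two | 0.073 | 0.085 | 0.091 |
| 10/40 | three | 0.087 | 0.113 | 0.126 |
| 25/25 | two | 0.073 | 0.083 | 0.091 |
| 25/25 | three | 0.088 | 0.111 | 0.126 |

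**3. If all three must be significant.** The false-positive chance drops to about 2% at correlation 0.9 and 0.3% at 0.5. Power for all three cannot exceed the power of the weakest one, so at the stated differences it is below 80% unless the metrics always agree.

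**4. Keeping all as primaries with Bonferroni.** Power at the stated differences (10/40; 25/25) is 70.5%; 70.7% for two (alpha 0.025) and 64.7%; 64.8% for three (alpha 0.0167).

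**5. Scale.** Testing both absolute and percent change of one metric adds little. The two rank patients almost identically (rank correlation 0.91–0.99 under assumed lognormal baselines), and the false-positive chance is about 6–7%.

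**6. Cutoff.** The plan says only that the threshold is optimal; maximum Youden J is assumed, with normal data, correlation 0.9 to 0.5 and equally predictive metrics.

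| Groups | Apparent J, one metric | Best of two | Best of three | True J |
|---|---|---|---|---|
| 25/25 | 0.417 | 0.445–0.466 | 0.460–0.491 | about 0.29 |
| 10/40 | 0.514 | 0.548–0.572 | 0.565–0.601 | about 0.35 |

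Picking the best metric therefore adds 0.03–0.06 (two) or 0.04–0.09 (three) to apparent J, and 0.01–0.04 to apparent PPV or NPV. If one metric is clearly better, with the others at about half its effect, it adds at most 0.02 to J. The larger gap is already there with one fixed metric: 0.417 − 0.29 ≈ 0.13 and 0.514 − 0.35 ≈ 0.16. It comes from choosing and evaluating the cutoff on the same patients.

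**7. Test against power.** The 80% is for a t-test. With normal data at the stated differences, the planned Wilcoxon test has about 77% (10/40) and 78% (25/25).

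**The case against.** The strongest reply is that this is a pilot with no success rule. The 0.05 level appears only in the power paragraph, and nothing says that one significant metric is enough. That stands. A reader might infer that the plan's false-positive rate simply is 9–13%; the documents do not support this, because the rate depends on a decision rule they never state. Nor do they support multiplying three metrics by two scales as if these were six loosely related tests, given step 5.

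The overall lesion average can also be read as the intended patient-level value, with individual lesions serving the heterogeneity aim (2.2). That is a fair reading. The text does not assign the average to the test, so this is an ambiguity rather than a contradiction. Likewise, T/M could be T/N with muscle as the reference, and since 6.5 compares only SUV and T/N, the two-metric figures may be nearer to what would be tested. But 6.5 does not make the link.

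What the reply does not meet is the missing variable itself. Even a purely exploratory cutoff has to be a cutoff of something, and the plan intends it for future use.

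**Conclusion.** The point holds as a specification gap of moderate consequence that should be closed before analysis. The size depends on the reading: about 7–9% (two metrics) or 9–13% (three) if any one counts, with the lower end more likely because the metrics share the tumor SUVmax; no inflation but power under 80% if all must succeed. Choosing the best metric for the cutoff adds modest optimism to the comparison with PgR by IHC. It does not explain the larger optimism from using the same patients to choose and evaluate the cutoff, and naming one variable will not remove that. The correlations, distributions and Youden criterion are assumptions. The documentary gaps and the power reproduction do not rest on them.

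A reader might also infer that the sample size is wrong. It is not: the stated differences are correct for a t-test on one variable.

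**What to change.** Before analysis:

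- In 10.1, name one metric, one scale and one patient-level lesion summary. An example is percent change in SUVmax averaged over up to 5 lesions; the choice of metric is the sponsor's.
- Say that lesions are selected on the baseline scan and that the same lesions are measured on both scans. Leaving the selecting scan open leaves a choice that can shift the change through regression to the mean.
- Use that variable for the single primary two-sided Wilcoxon test at 0.05 and for the ROC cutoff compared with PgR by IHC. Label the other metrics, the other scale and the other lesion summary secondary.
- State that the 80% power at 1.01 and 0.809 SD is for a t-test on that variable, and that Wilcoxon power is about 77–78% for normal data.
- Define T/M in 6.5 or delete it from 10.1.

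The cost is wording in 10.1 and 6.5; sample size, scans and data collection are unchanged. The downside is that the other metrics lose primary status. If one of them performs better, a cutoff from it would be hypothesis-generating only.

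### The power statement is for a t-test but the planned test is the Wilcoxon rank sum test, which under the same normal, equal-SD model has about 76-78% power at the stated differences, not 80%

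*Combined protocol and SAP*

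**What the plan says.** The Power Analysis paragraph of section 10.1 names its method: "Using a 2-sided independent t-test with 80% power at a 0.05 significance level". It works through two cases, the ends of an assumed 20-50% response rate. In the first, "a sample of 10 responders vs. 40 non-responders (i.e., 20% response rate") "will allow us to detect a minimum of 101% SD between-group difference". In the second, 25 against 25, the detectable difference is 80.9% SD. The SD is defined as the pooled SD of the uptake changes over responders and non-responders. No separate group SDs and no distribution for the change are given.

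The Data Analysis paragraph that follows names a different test for the same comparison. The changes in uptake "will be compared between responders and non-responders via" the "Wilcoxon rank sum test". The power figures carry no adjustment for the rank test, and its power is not stated anywhere. The section describes the study as a pilot with non-random sampling.

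**The concern.** A power statement describes the test it was computed for. When the data follow the t-test's own assumptions, the Wilcoxon test is slightly less efficient, so it needs a somewhat larger difference for the same power. The paragraph is the only quantitative support for enrolling 50 patients, and it describes a test that will not be run for this comparison.

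The calculation also relies on equal spread in the two groups. The scientific rationale gives some reason to doubt that. Sections 1.3 and 2.0 expect uptake to rise after estradiol in tumours with functional receptors, and in the mouse model the tumour-to-muscle ratio went from 3.6 to 6.9 in the endocrine-responsive line. A varied rise in one group and little change in the other would tend to give unequal SDs. With 10 against 40, the pooled SD then mostly reflects the non-responders.

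**Working it through.** **Inputs, all from section 10.1.** Two-sided alpha 0.05; power 80%; group sizes 10/40 and 25/25; stated differences d = 1.01 and 0.809 in pooled-SD units.

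**Step 1. Reproduce the stated figures.** For the t-test the noncentrality is d / √(1/n₁ + 1/n₂), with 48 degrees of freedom.

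- 10 vs 40: √(0.1 + 0.025) = 0.3536; 1.01 / 0.3536 = 2.857; power 79.9%. The difference giving 80% is 1.011.
- 25 vs 25: √(0.04 + 0.04) = 0.2828; 0.809 / 0.2828 = 2.860; power 80.0%. The difference giving 80% is 0.809.

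Both stated figures reproduce.

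**Step 2. Same model, planned test.** For normal data the large-sample efficiency of the Wilcoxon test relative to the t-test is 3/π = 0.955. Multiplying the noncentrality by √0.955 = 0.977 gives 2.79 in both cases, and power of about 78%. Simulation at the actual group sizes (normal, equal SD, 200,000 runs, Monte Carlo error about 0.1 point) gives the values below. The ranges run from the test with continuity correction to the test without it.

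| Case | d | t-test power | Wilcoxon power | d for 80% Wilcoxon power |
|---|---|---|---|---|
| 10 vs 40 | 1.01 | 79.9% | 76.5-77.4% | about 1.04-1.06 |
| 25 vs 25 | 0.809 | 80.0% | 77.2-77.9% | about 0.83-0.84 |

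**Step 3. Unequal spread (assumed SD ratios, normal changes).** The pooled SD is held at 1, as section 10.1 defines it. At 10 vs 40 and a responder-to-non-responder ratio of 2, the SDs are 1.60 and 0.80: (9 × 1.60² + 39 × 0.80²) / 48 = 1. At a ratio of 1.5 they are 1.35 and 0.90. Results are without continuity correction (60,000 runs each); the correction lowers the Wilcoxon figures by about one point or less.

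| SD ratio | Wilcoxon, 10 vs 40 | t-test, 10 vs 40 | Wilcoxon, 25 vs 25 |
|---|---|---|---|
| 1.5 | 64.2% | 74.8% | 77.7% |
| 2 | 56.3% | 71.8% | 77.0% |
| 3 | 48.9% | 68.9% | 76.0% |

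**Step 4. Other shapes (assumed, equal SD, pure shift).** Wilcoxon power at the stated differences for 10 vs 40 and 25 vs 25:

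- t distribution with 5 df: 84.9% and 86.4%
- Laplace: 86.8% and 88.9%
- right-skewed gamma (shape 2): 91.7% and 89.3%

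**The case against.** The strongest reply is that the plan's numbers are right for what it says it computed. A t-test approximation is a common way to size a pilot that will be analysed by ranks. The shortfall under normality is small beside the plan's own uncertainty: the stated range from 80.9% to 101% SD spans 20.1% of an SD, about five times the 4% correction at 10 vs 40. The plan names no target difference and gives no SUV value for the SD, so moving from 101% to 105% SD changes no decision. All of this stands, and it is why the point is minor.

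It also rules out three stronger readings that a reader might infer.

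- *The 101% and 80.9% figures are arithmetic errors.* They are not; Step 1 reproduces both. The fault is a mismatch between the test used for power and the test planned for analysis.
- *Power is about 77% outright, so the plan errs in its own favour.* That holds only for normal changes with equal SDs. The document states no distribution, and the equal-SD shapes in Step 4 give 85-92%, above the claimed 80%.
- *Power falls substantially whenever responders vary more.* With normal changes and the pooled SD fixed, the large loss is confined to 10 vs 40. Part of it also affects the t-test, so it cannot all be charged to the change of test. The SD ratios are assumptions. Other assumed combinations of skewness and unequal SD gave anything from 48% to 96%, so no single figure of this kind should be presented as the study's power.

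What remains is the mismatch itself. No section reconciles the two tests, and the stated 80% is not what the planned test delivers under the calculation's own model.

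**Conclusion.** The point holds in a limited form. Under normal changes with a common SD, the Wilcoxon test has about 76-78% power at the stated differences and needs about 105% SD (10 vs 40) and 84% SD (25 vs 25) for 80%. This rests on the model implied by the t-test calculation and on no outside figure.

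Beyond that model, the direction is not determined by the document. Heavy-tailed or skewed shifts could raise power. A larger responder SD would lower it at 10 vs 40, to about 56-64% for an assumed ratio of 1.5 to 2, while with normal changes 25 vs 25 stays at about 77-78%. The 10 vs 40 sensitivity deserves a sentence because that split is one of the plan's own two cases. Severity is minor: the design, the sample size and the choice of test are not in question.

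**What to change.** Rewrite the Power Analysis paragraph of section 10.1 for the Wilcoxon rank sum test. State that, for normally distributed changes with equal SDs in the two groups, 50 patients give 80% power at two-sided 0.05 for a difference of about 105% SD with 10 vs 40 and about 84% SD with 25 vs 25.

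Add a sentence that power could be higher if the changes are heavy-tailed or skewed, and that the 10 vs 40 case is sensitive to a larger responder SD. If the 56-64% figure is quoted, label it as an illustration, with its assumed SD ratio of 1.5 to 2 and fixed pooled SD.

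The cost is one paragraph and slightly less favourable figures. Sample size, planned test and study conduct do not change.
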